## **5.5 PHARMACODYNAMICS**

### **Complete depletion of CD19+ cell count**

Complete depletion of CD19+ cell count at any post-dose time is defined as CD19+ cell counts  $< 20$  cell/uL ( $0.02 \times 10^9$  cell/L). Subjects with missing CD19+ cell count at baseline or subjects with CD19+ cell count  $< 20$  cell/uL at baseline will be excluded from the derivation of complete depletion of CD19+ cell count.

### **Duration of CD19+ B-cell complete depletion**

This variable will be defined only for subjects who had a CD19+ B-cell complete depletion for at least one post-dose time. It is defined as time from the first incidence of complete depletion of CD19+ cell count to when CD 19+ cell count first increases to  $\geq 20$  cell/uL. Subjects whose CD 19+ cell count doesn't increase to  $\geq 20$  cell/uL will be censored at the last CD19 assessment date.

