**FOR CD19+, IGA, IGM AND IGG ANALYSIS:**

Study Analysis	Target Day	Study Day	Interval (days)
Visita			
Baseline b	1	≤1	NA
Day 2	2	2	1
Day 3	3	3	1
Week 4	29	15 – 42	28
Week 24	169	106 – 210	98
Week 48	337	≥309	NA

a IgG and IgA will not be collected at Day 2 and Day 3

b If a subject has measurements on the same day as the first infusion date of first dose but at a time after the first infusion of first dose is administered, the measurements will not be defined as baseline, but as Day 2 measurement.

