## 9.6 PHARMACODYNAMICS ANALYSES

All pharmacodynamics analyses will be performed using the FAS according to randomized treatment.

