### 9.6.1 CD19

The pharmacodynamics similarity will be evaluated descriptively for the difference in percent of subjects with complete CD19+ cell depletion between test (ABP 798) and reference (US-licensed rituximab or EU-authorized rituximab) from day 1 to day 3. Subjects with baseline value less than 20 cell/uL or missing will not be evaluable for CD19+ depletion analyses. The point estimate, the 90% CI and the 95% CI will be provided for rate difference and will be estimated using a generalized linear model (specifically, a log-binomial regression model) with stratification factors as covariates. A sample SAS code for PROC GENMOD is displayed below:

CCI

Note: The contrasts in the estimate statement may need to be changed depending on the order of the treatments.

Descriptive statistics for CD19+ counts as well as change from baseline will be provided at day 2 and day 3.

In addition, for duration of CD19 complete depletion, KM estimates and 90% CIs will be calculated by randomized treatment group for event time quartiles.

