**14.10 Immunogenicity Data Table**

Table 14-10.1.1. Anti-drug Antibodies Summary Results by Treatment- Day 1 Until 1st Infusion of the 2nd Dose (ADA Analysis Set)

Sponsor: Amgen Inc.

Statistical Analysis Plan

Protocol No: 20130108

10-December-2018/ Version 2.0

---

Table 14-10.1.2.	Anti-drug Antibodies Summary Results by Treatment- Entire Study (ADA Analysis Set)
14.11	Pharmacodynamics
Table 14-11.1.1.	Pharmacodynamics Results by Visit (Full Analysis Set)
Table 14-11.2.	Analysis of CD19+ Complete Depletion by Visit (Full Analysis Set)
Table 14-11.3.	Duration of CD19+ Complete Depletion (Full Analysis Set)
16.1	Study Information Listings
Listing 16-1.6.1.	Listing of Unique Manufacturing Lot Numbers
Listing 16-1.6.2.	Listing of Subjects Receiving Investigational Product – Subject Listing of Manufacturing Lot Numbers (Safety Analysis Set)
Listing 16-1.7.	Randomization Assignments (All Randomized Subjects)
16.2	Subject Data Listings
Listing 16-2.1.1.	Subject Listing of Disposition (All Randomized Subjects)
Listing 16-2.1.2.	Subject Listing of Screen Failures (All Screened Subjects)
Listing 16-2.2.	Important Protocol Deviations (Full Analysis Set)
Listing 16-2.3.	Inclusion/Exclusion Criteria Protocol Deviations (Full Analysis Set)
Listing 16-2.4.	Deviation/Exclusion From Analysis Populations (All Randomized Subjects)
Listing 16-2.5.	Investigational Product Administration (Safety Analysis Set)
Listing 16-2.6.1.	Blood Sampling Times and Serum ABP 798 and Rituximab Concentration Data (PK Concentration Analysis Set)
Listing 16-2.6.2.1	Individual PK Parameters from PK Analysis of ABP 798 (PK Parameter Analysis Set)
Listing 16-2.6.2.2.1	Individual PK Parameters from PK Analysis of Rituximab (US) (PK Parameter Analysis Set)
Listing 16-2.6.2.3.1	Individual PK Parameters from PK Analysis of Rituximab (EU) (PK Parameter Analysis Set)
Listing 16-2.7.1.	Subjects Who Experienced Treatment-emergent Adverse Events Leading to Discontinuation of Study IP/Study (Safety Analysis Set)
Listing 16-2.7.2.	Subjects with Treatment-emergent Adverse Events with Fatal Outcome (Safety Analysis Set)

Sponsor: Amgen Inc.

Statistical Analysis Plan

Protocol No: 20130108

10-December-2018/ Version 2.0

---

Listing 16-2.7.3.	Subjects Who Experienced Serious Treatment-emergent Adverse Events (Safety Analysis Set)
Listing 16-2.8.1.	Subjects Who Experienced a Grade $\geq 3$ Hematology Result (Safety Analysis Set)

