## **APPENDIX 7 SHELLS FOR POST-TEXT TABLES, FIGURES, AND LISTINGS**

See associated TFL shell document.

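### CD19 depletion duration has no cut at the second dose, so the later quartiles for the rituximab (US) arm would partly describe retreatment with ABP 798

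*SAP*

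**What the plan says.** SAP 4.2.3 lists duration of complete CD19+ depletion as a pharmacodynamic endpoint. The Protocol's own PD endpoint (8.6.1.1) covers only days 1 to 3, so duration enters with the SAP and no Protocol rule governs it.

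SAP 5.5 runs the time from the first count below 20 cells/uL to the first count at or above it. Subjects who never recover to 20 "cell/uL will be censored at the last CD19 assessment date".

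SAP 9.6 states: "All pharmacodynamics analyses will be performed using the FAS according to randomized treatment". For duration, 9.6.1 adds that "KM estimates and 90% CIs will be calculated by randomized treatment group for event time quartiles". The result is Table 14-11.3.

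Under SAP 3, group B (rituximab US) receives ABP 798 as its second dose at week 24, or from week 16 if the investigator judges it necessary. Groups A and C stay on the same product.

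Other parts of the SAP do separate the two dosing periods:
- SAP 9.7 drops efficacy data after the first infusion of the second dose for the week 24 analysis.
- SAP 9.8 gives safety summaries up to that infusion.
- Table 14-9.1.2 names both products for the US arm.
- SAP 9.4 uses sequence labels such as rituximab (US)/ABP 798.

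SAP 5.1 limits the week 24 record to visits on or before the second dose. That rule selects a visit record; it does not end a time-to-event variable.

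**The concern.** Three columns of depletion quartiles by randomised arm invite a reader to compare B-cell recovery after ABP 798 with recovery after each reference product. The later quartiles cannot support that comparison. In every arm they mix first-dose and second-dose effects. In the rituximab (US) column the second-dose effect belongs to the test product, so agreement between the ABP 798 and US columns late in follow-up would partly compare ABP 798 with itself.

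**Working it through.** The documents give no figure for CD19 duration, so there is nothing to reproduce. The check is whether the stated rule and the sampling schedule make the quartiles depend on data after the second dose.

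**Inputs from the documents**
- CD19 samples: baseline, days 2 and 3, and weeks 4, 24 and 48/EOS (Protocol Table 1).
- The week 24 sample is taken before dosing (Protocol 9.11). With early retreatment it moves up with the visit, and EOS falls 24 weeks after the second dose starts (Table 1, footnote a).
- Protocol 6.2: in most treated patients, peripheral B-cell depletion lasted six months or longer.

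**Step 1: thresholds.** Let f be the share of subjects in the duration analysis with no recovery recorded by the pre-second-dose sample. With complete follow-up, KM survival there equals f. A quartile is free of post-second-dose data only if it is reached by then:
- Q1 needs f ≤ 75%.
- The median needs f ≤ 50%.
- Q3 needs f ≤ 25%.

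If most patients stay depleted for six months, f exceeds 50% at week 24, and both the median and Q3 fall after the second dose.

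**Step 2: what then decides the quartile.** Let p be the share of those still depleted, all assumed retreated, who have recovered at EOS. Survival at EOS is f(1 − p). Put first depletion on day 2, the pre-dose sample on day 169 (167 days later) and EOS on day 337 (335 days later). Hold f at 0.60 (assumed):

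| p | Survival at EOS | Q1 | Median | Q3 |
|---|---|---|---|---|
| 0.10 | 0.60 × 0.90 = 0.54 | 167 | not reached | not reached |
| 0.50 | 0.60 × 0.50 = 0.30 | 167 | 335 | not reached |
| 0.70 | 0.60 × 0.30 = 0.18 | 167 | 335 | 335 |

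First-dose behaviour is identical in all three rows. The median and Q3 change only through what happens after the second dose. By contrast, if f were 0.20, all three quartiles would be 167 days and the issue would not arise.

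A simulation gave the same picture for Q3. It used 400 runs, 100 subjects per arm, the pre-dose sample on day 169 ± 2 and EOS 168 days later ± 2, with f = 0.60. If 30% of retreated subjects are still depleted at EOS, Q3 is 336 days. If 90% are, Q3 is not reached in roughly nine runs in ten (88% to 92% in separate runs).

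**Step 3: how many subjects.** The number whose time rests on post-second-dose data is N × f × r, where r is the share of still-depleted subjects who are retreated. Assume f of 0.55 to 0.70 and r of 0.85 to 1.00:
- N = 100 (all randomised): 47 to 70.
- N = 85 (15% dropout): 40 to 60.
- N = 70 (also allowing, by assumption, for subjects that SAP 5.5 excludes for missing or low baseline CD19): 33 to 49.

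**Step 4: why a simple cut is not the remedy.** If KM is censored at the pre-dose sample, that sample supplies both the recoveries and the censorings. Take 100 subjects with f = 0.60.
- All sampled at the same duration: 40 events among 100 at risk, so survival is 0.60, which is correct.
- Half sampled at 166 days and half at 168: 20 events of 100 gives 0.80; 30 are censored; then 20 events of 50 gives 0.80 × 0.60 = 0.48.
- Four equal groups on successive days: 0.900 × 0.867 × 0.800 × 0.600 = 0.37.

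The bias is always downward and grows with the timing spread. In simulation with f = 0.55, the final estimate was 0.55 with no spread, about 0.24 with ± 2 days and about 0.15 with ± 7 days. Protocol 9.11 gives no window for week 24, so these sizes are illustrations.

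**Step 5: precision of the alternative.** For a difference in percent still depleted at f = 0.60, the 90% CI half-width is 1.645 × √(2 × 0.60 × 0.40 / n). That is 12.4 points with 85 per arm and 13.6 with 70.

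**The case against.** The strongest reply is that nothing here is wrong as an as-randomised summary. Group B is randomised to a sequence that includes ABP 798, the full analysis set follows assignment, and SAP 4.2.3 and 5.5 never call duration a first-dose measure. Following the assigned sequence to EOS is a legitimate target. This stands: the summary can stay if it is labelled as a sequence and said to include retreatment. The SAP text does neither.

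A second reply is that the answer may lie in material not seen here. Appendix 7 says only "See associated TFL shell document", so the column headings of Table 14-11.3 are unknown. Tables 14-11.1.1 and 14-11.2 are both titled by visit, and SAP 5.1 defines a week 24 CD19 window of days 106 to 210, so a pre-second-dose view may already be planned. A reader might infer from the SAP that no such view exists; the documents do not establish that. They do not establish the opposite either: 9.6.1 limits the depletion comparison to days 1 to 3 and says "Descriptive statistics for CD19+ counts as well as change from baseline will be provided at day 2 and day 3".

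A third reply is that no decision rests on this table. That also stands. It would be tempting to read the mixing of products as a threat to the biosimilarity conclusion. The documents do not support this, because no between-arm contrast of duration is planned and no decision rule uses it.

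**Conclusion.** The point holds as a defect of definition and labelling in one descriptive PD table. As written, the median and Q3 of CD19 depletion duration cannot be read as first-dose results in any arm, and in the rituximab (US) arm they partly describe ABP 798. Which quartiles are affected depends on f, which the documents do not give. Protocol 6.2 points to f above 50%, so the median and Q3 are the likely ones; Q1 is affected only if f exceeds 75%. Subjects who are never retreated, and those who recover by the pre-second-dose sample, are unaffected.

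The threshold argument needs only complete follow-up to the pre-second-dose sample. The worked quartiles and subject counts rest on assumed values of f, p and r, and the simulated figures also on an assumed spread of sample days. The change is worth making before unblinding, but it does not bear on the trial's main conclusions.

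**What to change.** 1. In SAP 9.6.1, add the percent of evaluable subjects still depleted at the last CD19 sample on or before the first infusion of the second dose, which is the week 24 record under SAP 5.1. Give the difference between ABP 798 and each reference with its 90% CI. If the shell of Table 14-11.1.1 or 14-11.2 already shows this at week 24, say so in 9.6.1 instead.
2. Keep the EOS quartiles in Table 14-11.3 only as a treatment-sequence summary. Label the columns ABP 798/ABP 798, rituximab (US)/ABP 798 and rituximab (EU)/rituximab (EU), as SAP 9.4 does, and state in 5.5 and 9.6.1 that the times include retreatment.
3. Do not replace the quartiles with an ordinary KM estimate censored at the pre-dose sample. If a first-dose time-to-recovery estimate is wanted, use an interval-censored method.

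The cost is SAP wording, a label change and at most one added descriptive output, all from data already collected. The first-dose summary ignores data after the second dose, but these remain in the sequence table.

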## **6. ANALYSIS SETS**

The primary statistical analysis for the PK endpoints will be based on the PK parameter analysis set. Sensitivity analysis for the PK endpoints will be based on the per-protocol (PP) PK parameter analysis set. The primary statistical analysis for the PD endpoint and efficacy endpoints will be performed using the full analysis set (FAS). The Per-protocol analysis set will be used for sensitivity analyses of the key efficacy endpoints. The analysis of safety endpoints will be based on the safety analysis set. The immunogenicity analysis will be based on anti-drug antibody analysis set.

### **6.1 FULL ANALYSIS SET**

The FAS includes all subjects randomized in the study, with treatment assignment based on treatment the subject is randomized to (regardless of actual treatment received).

Sponsor: Amgen Inc.

Statistical Analysis Plan

Protocol No: 20130108

10-December-2018/ Version 2.0

## 6.2 PER-PROTOCOL ANALYSIS SET

The per-protocol (PP) analysis set includes all randomized subjects who have had two full infusions for the 1st dose (drug compliance of 90%-110%), have completed the week 24 disease assessment (complete DAS28-CRP assessment in the week 24 window of day 106-210 and before the 1st infusion of the 2nd dose), and did not experience a protocol deviation up to week 24 that affects their evaluation for the secondary objectives of the study to assess clinical efficacy. The protocol deviations that affect evaluation of the secondary objectives will be determined based on a blinded data review prior to database lock. Analyses for the per-protocol analysis set will be based on actual treatment received.

## 6.3 SAFETY ANALYSIS SET

The safety analysis set includes all randomized subjects who received at least 1 infusion of IP, with treatment assignment based on actual treatment received.

## 6.4 PHARMACOKINETIC CONCENTRATION ANALYSIS SET

The PK concentration analysis set is defined as the subset of subjects in the safety analysis set who received the full protocol-specified dose on Day 1 and had at least one evaluable serum concentration (including results below the quantifiable limit) of ABP 798 or rituximab. Pharmacokinetic concentration data from subjects will be analyzed according to the actual treatment received. Subjects to be excluded from the PK concentration analysis set will be determined based on a blinded data review prior to database lock.

## 6.5 PHARMACOKINETIC PARAMETER ANALYSIS SET

The PK parameter analysis set is defined as the subset of subjects in the safety analysis set who received the full protocol-specified dose on Day 1 and had an evaluable ABP 798 or rituximab serum concentration time profile. The PK parameter analysis set will be used for the primary statistical analysis of PK endpoints. Pharmacokinetic parameter data from subjects will be analyzed according to the actual treatment received. Subjects to be excluded from the PK parameter analysis set will be determined based on a blinded data review prior to database lock.

## 6.6 PER-PROTOCOL PHARMACOKINETIC PARAMETER ANALYSIS SET

The per-protocol PK parameter analysis set consists of a subset of subjects in the PK parameter analysis set who do not experience an important protocol deviation that affects their PK evaluation. It will be analyzed according to actual treatment received. The important protocol deviations that affect evaluation of PK endpoints will be determined based on a blinded data review prior to database lock.

Sponsor: Amgen Inc.

Statistical Analysis Plan

Protocol No: 20130108

10-December-2018/ Version 2.0

## 6.7 ANTI-DRUG ANTIBODY ANALYSIS SET

Anti-drug antibody analysis set is defined as the subset of subjects in the safety analysis set who had at least 1 evaluable antibody test. Immunogenicity data from subjects will be analyzed according to the actual treatment received.

## 7. INTERIM ANALYSES

No interim analyses are planned for this study.

A Data Monitoring Committee (DMC) external to Amgen and PRA will be formed with members consisting of individuals chosen for their expertise in inflammatory disorders. Members of the DMC will include, at a minimum, physicians external to Amgen and PRA, and appropriate statistical representation external to Amgen and PRA. The primary role of this independent DMC will be to monitor safety data.

The DMC will review unblinded safety data at regular intervals, as outlined in the DMC charter (approximately twice yearly; the start date will depend on subject accrual rates). The DMC will also review an initial safety analysis after the first 18 subjects have received the first dose.

In addition, the DMC will communicate major safety concerns and recommendations regarding study modification or termination to Amgen management at any time during the conduct of the study.

Details regarding the DMC will be provided in the DMC charter and DMC analysis plan.

## 8. DATA REVIEW

### 8.1 DATA HANDLING AND TRANSFER

Data will be entered and exported as SAS® version 9.4 or higher datasets. Converted datasets will be created using SAS® and following standard Clinical Data Interchange Standards Consortium Standard Data Tabulation Model (CDISC SDTM, version 1.3, Implementation Guide version v3.1.3) conventions. Analysis datasets will be created using SAS® and following CDISC Analysis Data Model (ADaM, version 2.1, Implementation Guide 1.0) standards.

Medical history and AEs will be coded using the current version of MedDRA at the time of the analysis to assign a system organ class (SOC) and preferred term (PT) to each event. Adverse events and abnormal laboratory results considered as AEs are assigned a toxicity grade according to National Cancer Institute (NCI-US) Common Terminology Criteria for Adverse Events (CTCAE). Prior and concomitant medications will be coded using the current version of the World Health Organization Drug Dictionary (WHO-DD) at the time of the analysis.

Additional details can be found in the PRA Data Management Plan for this study.

Sponsor: Amgen Inc.

Statistical Analysis Plan

Protocol No: 20130108

10-December-2018/ Version 2.0

---

## 8.2 DATA SCREENING

Beyond the data screening built into the PRA Data Management Plan, the PRA programming of analysis datasets and tables, figures and listings (TFLs) provides additional data screening as described below.

Review of a post-freeze dry run of TFLs allows for further data screening prior to final database lock for the entire study. This dry run will be discussed with the sponsor in data review meetings to identify any final data issues and seek corrections prior to the final database lock for the entire study. The PRA statistician and the sponsor must approve database lock.

## 9. STATISTICAL METHODS

All statistical analyses will be performed using SAS® (Version 9.4 or higher).

The final analysis will be performed after all subjects have completed or have had the opportunity to complete the week 48/EOS assessment.

Unless otherwise specified, descriptive data summaries will be tabulated by treatment for all endpoints. Categorical data will be summarized using number of subjects (n), frequency and percentages of subjects falling into each category, with the denominator for percentages being the number of subjects in the study population for each treatment group, unless otherwise noted. Percentages will be rounded to one decimal place. Confidence intervals will be provided where specified.

All continuous variables will be summarized using mean, standard deviation, median, minimum, maximum, 25th percentile (Q1), 75th percentile (Q3), and number of subjects with observations. The mean, median, Q1, and Q3 will be presented to one decimal place greater than the original data, standard deviation will be to two decimal places greater than the original data, and the minimum and maximum will have the same number of decimal places as the original data. Confidence intervals will be provided where specified.

For any of the summaries that are to be done by visit, the derived analytical study visit as defined in [section 5.1](#) will be used for analysis unless otherwise noted.

## 9.1 SUBJECT DISPOSITION

The following information will be summarized for subject disposition and accountability:

- Number of subjects randomized will be tabulated by region, country and center based on the FAS.
- Number of subjects randomized will be tabulated by stratification factors based on the FAS.
- Subject disposition (including number randomized, treated with ABP 798/rituximab (US)/rituximab (EU), completed treatment, discontinued treatment with reason of discontinuation, completed study, and discontinued study with reason of discontinuation) using each of the analysis sets defined in [Section 6](#).

Sponsor: Amgen Inc.

Statistical Analysis Plan

Protocol No: 20130108

10-December-2018/ Version 2.0

---

- Summaries of analysis sets with reason for exclusion for all screened subjects.
- Randomization list of subjects and their actual versus randomized treatment group for all randomized subjects.

## 9.2 PROTOCOL DEVIATIONS

Protocol deviation (PD) data will be entered into the Clinical Trials Management System (CTMS). The study team will conduct on-going reviews of the PD data from CTMS. The per-protocol analysis set and per protocol PK parameter analysis set must be finalized at the post-freeze data review meeting (or earlier), prior to the database lock.

Based on the PD data entered into CTMS, a summary of important PDs will be tabulated using number and percentage of subjects with important PD by deviation type and randomized treatment arm. A listing of subjects with important PDs will be provided (with a flag indicating whether the deviation leads to exclusion from the per-protocol and per-protocol pharmacokinetic analysis sets). A summary table and listing of eligibility criteria deviations will also be tabulated showing the violations of the inclusion/exclusion criteria for each subject.

